6.1. Statistical Considerations for Primary Objective

The primary objective of this study is to assess objective response rate (ORR) following the administration of axitinib for 12 weeks in patients with locally advanced biopsy-proven clear cell renal cell carcinoma prior to undergoing radical nephrectomy.

Twenty-four patients will be treated in this study. We plan to abort recruitment should we have reason to believe that axitinib does not provide minimal efficacy, defined as $\Pr[\text{ORR} \geq 20\% \mid \text{data}] < 5\%$. We also plan to stop recruitment should we have reason to believe that it may be harmful, defined as $\Pr[\text{PD} > 20\% \mid \text{data}] > 80\%$, where PD is progressive disease. We will monitor study patients using the Bayesian approach of Thall¹². ORR will be evaluated at week 12 following initiation of treatment and PD will be evaluated at week 7 and week 12 following initiation of treatment.

For calculating our stopping criteria and operating characteristics for futility and disease progression, we assume that $\text{ORR} \sim \text{Beta}(0.4, 1.6)$ and $\text{PD} \sim \text{Beta}(0.4, 1.6)$. The prior for both ORR and PD has a mean of 20% and a standard deviation of 23%.

We will continually evaluate patients for excessive PD as they are being enrolled. We will begin evaluating for minimal ORR after the first 18 patients have been treated and evaluated for responses. Given that those patients who have PD will be immediately terminated from the study treatment to have a nephrectomy, we do not feel that delaying evaluation for futility until 18 patients are treated will jeopardize patient wellbeing. Once the minimum number of patients has been treated and assessed for ORR and PD, we will continue to assess both outcomes after each additional patient has been evaluated.

The trial will be stopped for futility (low ORR) if

$$[\# \text{ of patients with ORR} / \# \text{ of patients evaluated at Week 12}] \leq 1/18.$$

Likewise, the trial will be stopped for excessive PD if

$$[\# \text{ of patients with PD} / \# \text{ of patients evaluated at Week 7 and 12}] \geq 3/6, 4/9, 5/13, 6/17, 7/21.$$

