To illustrate the use of these stopping rules, suppose 18 patients are treated in this study and evaluated for response and only 1 had ORR. We would close the study for lack of efficacy. If 2 patients out of the first 18 respond, then an additional 6 patients will be treated for a total of 24 patients. Likewise, if 6 out of 17 patients had PD, we would close the study for excessive PD.

The operating characteristics for the futility monitoring rule are shown in Table 1 and for the PD monitoring rule are shown in Table 2. The operating characteristics in Table 1 do not

account for early stopping due to excessive PD; likewise, the operating characteristics in Table 2 do not account for early stopping due to futility.

We plan to stop recruitment if we observe 2 treatment-related deaths. Treatment-related deaths are defined as deaths directly caused by study drug while the patients are taking the study drug, or intraoperatively, or within 30 days after nephrectomy, and the decision to classify the deaths as directly caused by study drug will be made by the study Principal Investigator. Perioperative mortality for patients undergoing radical nephrectomy is estimated to be between 1% and 4%¹³⁻¹⁵. The operating characteristics associated with this decision criterion are shown in Table 3. These probabilities were derived by running 1,000 simulations.

We also plan to stop recruitment if two or more patients a) cannot undergo radical nephrectomy as a result of participating in the study, or b) experience a delay in time to radical nephrectomy of more than 6 weeks from last axitinib dose, or c) experience inadequate healing post-operatively defined as fascial dehiscence requiring reoperation, or d) experience severe bleeding post-operatively defined as bleeding requiring reoperation.

Table 1. Operating Characteristics of the ORR Futility Monitoring Rule

Success Rate	Probability of Stopping Early	Sample Size		
		P ₂₅	P ₅₀	P ₇₅
0.05	0.775	18	18	18
0.10	0.455	18	24	24
0.15	0.221	24	24	24
0.20	0.106	24	24	24
0.25	0.039	24	24	24

Table 2. Operating Characteristics of the Excessive PD Monitoring Rule

Success Rate	Probability of Stopping Early	Sample Size		
		P ₂₅	P ₅₀	P ₇₅
0.10	0.056	24	24	24
0.15	0.165	24	24	24
0.20	0.346	12	24	24
0.25	0.537	8	19	24
0.30	0.724	6	11	24

Table 3. Operating Characteristics of the Treatment-Related Mortality Stopping Rule

$\pi_{\text{treatment-related mortality}}$	Probability of Stopping Early	Sample Size		
		P ₂₅	P ₅₀	P ₇₅

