7.2. Treatment Phase

7.2.1. Eligible patients will provide written informed consent.

7.2.2. Prior to the initiation of therapy, a surgical date will be established.

7.2.3. Treatment Assignment: Each patient will receive a total of 12 weeks of axitinib. Patients will take the last dose of axitinib 1.5 days prior to surgery.

7.2.4. Adverse events monitoring and reporting:

7.2.4.1. Adverse events:

7.2.4.1.1. The investigator is responsible for determining the attribution of adverse events to study drug.

7.2.4.1.2. Adverse events will be documented in the medical record and entered into the case report form according to the Recommended Adverse Event Recording Guidelines for Phase II protocol (see table below).

Recommended Adverse Event Recording Guidelines					
Attribution	Grade 1	Grade 2	Grade 3	Grade 4	Grade 5
Unrelated	Phase I	Phase I	Phase I Phase II	Phase I Phase II Phase III	Phase I Phase II Phase III
Unlikely	Phase I	Phase I	Phase I Phase II	Phase I Phase II Phase III	Phase I Phase II Phase III
Possible	Phase I Phase II	Phase I Phase II Phase III	Phase I Phase II Phase III	Phase I Phase II Phase III	Phase I Phase II Phase III
Probable	Phase I Phase II	Phase I Phase II Phase III	Phase I Phase II Phase III	Phase I Phase II Phase III	Phase I Phase II Phase III
Definitive	Phase I Phase II	Phase I Phase II Phase III	Phase I Phase II Phase III	Phase I Phase II Phase III	Phase I Phase II Phase III

7.2.4.1.3. Adverse events will be assessed at each patient visit, documented in the medical record, and entered into the CRFs. Adverse events should be treated appropriately. Such treatment may include changes in axitinib treatment including possible interruption or discontinuation, starting or stopping concomitant treatments, changes in the frequency or nature of assessments, hospitalization, or any other medically required intervention. Once an adverse event is detected, it should be followed until its resolution, and assessment should be made at

each visit of any changes in severity, the suspected relationship to the axitinib, the interventions required to treat it, and the outcome. In addition, Pfizer requires reporting of serious adverse events on the M.D. Anderson SAE forms. Reporting of adverse events will be done according to NCI Common Terminology Criteria for Adverse Events (CTCAE) version 4.0. The following items will be recorded at least:

- Event description
- Date of onset of AE
- CTCAE grade/severity (1,2,3,4,5)

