7.2.6.1. Axitinib dose increase: Because previous studies indicated variable drug levels in patients, the axitinib dose will be increased in a step-wise fashion from 5 mg twice daily to 7 mg twice daily, then to 10 mg twice daily, in the absence of axitinib-related toxicity greater than or equal to grade 2 for a continuous 2-week period and in the absence of hypertension (defined as two blood pressure [BP] measurements of > 150/90 mmHg taken in the clinic > 1 hour apart) at any point during study. The clinical judgment of the treating physician should be exercised in up-titrating the axitinib dose.

7.2.6.2. Axitinib dose modifications for adverse events (other than hypertension and proteinuria):

7.2.6.2.1. Patients developing axitinib-related CTCAE Grade 1 adverse events may have their dose increased to next dose level.

- 7.2.6.2.2. Patients developing axitinib-related CTCAE Grade 2 adverse events should have their dose continued at the same dose level.
- 7.2.6.2.3. Patients developing axitinib-related CTCAE Grade ≥ 3 adverse events should have their dose reduced as indicated in section 7.2.6.2.6
- 7.2.6.2.4. If patients need to have their axitinib treatment interrupted for 2 or more continued-week period due to unmanageable toxicities or any other reason, their axitinib treatment will be permanently discontinued and considered treatment failures. Patients will then proceed to surgery to have their kidney tumors removed.
- 7.2.6.2.5. Patients removed from treatment for intolerable toxicity should still be followed with regular tumor assessments (every 4 months for 1 year, every 6 months for the next 2 years and every 12 months for one more year) until disease progression or start of new treatment, and for survival thereafter until study completion.
- 7.2.6.2.6. The criteria for dose modification for study-drug-related adverse events are summarized in the table below:

CRITERIA FOR DOSE MODIFICATION FOR AXITINIB-RELATED ADVERSE EVENTS OTHER THAN HYPERTENSION OR PROTEINURIA	
Related Adverse Events	INTERVENTION
Grade 1	Increase to next dose level, or maintain if already at the maximum dose
Grade 2	Continue at same dose level
Grade 3 nonhematologic treatment-related toxicity* or Grade 3 hematologic toxicity	Decrease dose to one lower dose level

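### The two-death stopping rule in section 6.1 does not count a drug-caused death that occurs after axitinib is stopped and before, or without, nephrectomy

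*Combined protocol and SAP*

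**What the plan says.** Section 6.1 (Statistical Considerations for Primary Objective) states: "We plan to stop recruitment if we observe 2 treatment-related deaths". The deaths that qualify are "deaths directly caused by study drug while the patients are taking the study drug, or intraoperatively, or within 30 days after nephrectomy". On attribution, "the decision to classify the deaths as directly caused by study drug will be made by the study Principal Investigator". Table 3 gives the operating characteristics, indexed by treatment-related mortality.

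The next paragraph of 6.1 adds a companion rule. Recruitment also stops if two or more patients (a) are unable to have the nephrectomy because they took part, (b) "experience a delay in time to radical nephrectomy of more than 6 weeks from last axitinib dose", (c) have a fascial dehiscence needing reoperation, or (d) have postoperative bleeding needing reoperation.

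Other sections determine how long a patient can be off drug before surgery:

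- Section 7.2.3, on schedule: "Patients will take the last dose of axitinib 1.5 days prior to surgery".
- Section 7.2.6.2.4, after an interruption of two weeks or more: "their axitinib treatment will be permanently discontinued and considered treatment failures". The patient then goes to surgery, and no maximum time to surgery is given there.
- Section 7.2.6.2.6: Grade 4 nonhematologic related toxicity leads to stopping axitinib, with a footnoted exception for asymptomatic laboratory abnormalities.
- Section 7.2.12: progression at week 7 leads to permanent discontinuation and earlier surgery.

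Section 7.2.4.2.2.3 captures serious adverse events from consent until 30 days after the last dose, requires later related events to be reported as well, and requires fatal events to reach the IND office within 24 hours whatever their attribution.

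**The concern.** All three windows are tied either to taking the drug or to the operation. A patient who has stopped axitinib and has not yet been operated on is in neither state, and a patient who is never operated on has no window after the last dose. Patients taken off drug for severe toxicity leave the first window at that moment. If one of them dies of that toxicity before surgery, the definition as written does not add the death to the count.

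This is the only stopping rule in 6.1 that names death, and its threshold is just two. One uncounted death can decide whether it fires. Two drug-caused deaths among 24 candidates for curative surgery could occur, and be known to the sponsor, without stopping recruitment under the written rules.

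**Working it through.** **Inputs.** Maximum sample size: "Twenty-four patients will be treated in this study" (6.1). Threshold: 2 deaths (6.1). Stated stopping probabilities: Table 3, of which 6.1 says "These probabilities were derived by running 1,000 simulations". Share of drug-caused deaths falling in the gap, *f*: not in the documents, so a range is assumed.

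**Step 1: reproduce Table 3.** If each patient has probability *q* of a countable death, independently,

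P(stop) = 1 − (1−q)^24 − 24·q·(1−q)^23.

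At q = 0.10: 1 − 0.0798 − 0.2127 = 0.708, equal to Table 3. Over the seven rates in Table 3 (0.5%, 1%, 2%, 4%, 7%, 10%, 20%) the exact values are 0.006, 0.024, 0.083, 0.249, 0.508, 0.708 and 0.967. Table 3 has 0.012, 0.033, 0.083, 0.268, 0.505, 0.708 and 0.976. All agree within 2 percentage points, so the table is a two-event rule in 24 patients.

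**Step 2: the death rule alone, with a gap.** If drug-caused mortality is *p* and a share *f* falls in the gap, the countable rate is q = p(1−f). For p = 0.10 and f = 0.5, q = 0.05 and P(stop) = 1 − 0.2920 − 0.3688 = 0.339.

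| True rate p | Table 3 | f = 0 | f = 10% | f = 25% | f = 50% |
|---|---|---|---|---|---|
| 4% | 0.268 | 0.249 | 0.213 | 0.161 | 0.083 |
| 7% | 0.505 | 0.508 | 0.452 | 0.361 | 0.205 |
| 10% | 0.708 | 0.708 | 0.649 | 0.546 | 0.339 |
| 20% | 0.976 | 0.967 | 0.946 | 0.894 | 0.708 |

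**Step 3: add companion rule (a), read to include death before surgery.** Let A, G and W be the numbers of drug-caused deaths on drug, in the gap, and perioperatively (during surgery or within 30 days after it). The death rule fires if A + W ≥ 2; rule (a) fires if A + G ≥ 2. With two or more deaths in total, the only outcome that fires neither is A = 0, G = 1, W = 1. The loss against counting every death is therefore

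24·23·(p·f)·(p·w)·(1−p)^22,

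where *w* is the perioperative share. At p = 0.10 and f = w = 0.5: 552 × 0.05 × 0.05 × 0.0985 = 0.136, and 0.708 − 0.136 = 0.572. With f = 0.5 throughout:

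| True rate p | All deaths count | Death rule alone | With (a): other half on drug | With (a): 25% on drug, 25% perioperative | With (a): other half perioperative |
|---|---|---|---|---|---|
| 4% | 0.249 | 0.083 | 0.249 | 0.204 | 0.159 |
| 7% | 0.508 | 0.205 | 0.508 | 0.440 | 0.371 |
| 10% | 0.708 | 0.339 | 0.708 | 0.640 | 0.572 |
| 20% | 0.967 | 0.708 | 0.967 | 0.947 | 0.926 |

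This step gives no credit for a perioperative death that also involved a (c) or (d) event. If items (a) to (d) are counted together, such a death pairs with the gap death and recruitment stops, so the loss is smaller than shown.

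**The case against.** The strongest reply has five parts.

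1. *Rule (a) already covers these deaths.* A patient killed by the drug before surgery cannot undergo nephrectomy because of participating, and the threshold is also two. This largely stands, and it means that the death-rule-alone figures should not be read as the trial's overall chance of stopping for fatal toxicity. But rule (a) does not name death, and its count is not added to the death count, so the one-plus-one case remains.

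2. *Table 3 is correct.* Its index can be read as the rate of deaths that meet the definition in the same section, and on that reading it describes the written rule exactly. This stands. Table 3 describes stopping for all drug-caused deaths only if the definition covers all of them.

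3. *Nothing goes undetected.* A reader might infer that these deaths are missed. They are not: section 7.2.4.2.2.3 requires them to be reported. What fails is the count, since reporting is not a stopping criterion.

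4. *The gap is usually short.* A reader might infer that fatal toxicity typically falls in it. The documents give no such frequency. The planned gap is 1.5 days; most Grade 3 events lead to dose reduction or continuation; Grade 4 hematologic events and blood pressure above 160/105 lead to interruption with a planned restart. The 6 weeks in item (b) is a trigger for stopping recruitment, not a scheduled interval. All of this stands, and the share in the gap may be small.

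5. *The first window could refer to when the harm was caused, not when death occurred.* This is possible, but the other two windows time the death, so it is the less natural reading. A stopping rule open to both readings needs clarifying in any case.

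**Conclusion.** The point holds as a gap in a safety definition, of moderate severity. As written, the two-death rule does not count a drug-caused death off drug and before, or without, nephrectomy, and no other section adds such a death to that count. One gap death plus one drug-caused perioperative death without a (c) or (d) event would stop the trial under neither rule.

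The size depends on two things that the documents leave open: the share of drug deaths in the gap, and whether rule (a) includes death. At 10% true mortality, if rule (a) is not read to include death, stopping falls from 0.708 to 0.649, 0.546 or 0.339 for shares of 10%, 25% or 50%. If it is, the 50% case lies between 0.572 and 0.708, so the loss runs from nothing to about 14 percentage points. These figures assume independent deaths, all 24 patients treated unless a rule fires, and correct attribution. The documents do not support the stronger conclusions that Table 3 is miscalculated or that the trial has no protection against fatal toxicity after the drug is stopped.

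**What to change.** In section 6.1, replace the three windows with one continuous window: count any death judged directly caused by study drug from first dose until 30 days after nephrectomy, or until 30 days after the last dose if nephrectomy is not done. The second limit matches the serious adverse event capture window in section 7.2.4.2.2.3. Keep the threshold of 2, the attribution procedure and Table 3 unchanged. It would help to say in the same place whether a death before surgery also counts under companion rule (a).

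One remainder should be decided openly: a drug-caused death more than 30 days after the last dose in a patient not operated on would still fall outside. Section 7.2.4.2.2.3 already requires related events after that time to be reported, so the information would exist if the sponsor wished to count them.

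The cost is one sentence, with no new visits or data. The downside is a higher chance of stopping than under the present wording, up to the level that Table 3 already states.

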7.2.4.2.2.3. Important medical events that may not result in death, be life-threatening, or require hospitalization may be considered a serious adverse drug experience when, based upon appropriate medical judgment, they may jeopardize the patient or subject and may require medical or surgical intervention to prevent one of the outcomes listed in this definition. Examples of such medical events include allergic bronchospasm requiring intensive treatment in an emergency room or at home, blood dyscrasias or convulsions that do not result in inpatient hospitalization, or the development of drug dependency or drug abuse (21 CFR 312.32):

- Important medical events as defined above, may also be considered serious adverse events. Any important medical event can and should be reported as an SAE if deemed appropriate by the Principal Investigator or the IND Office .
- All events occurring during the conduct of a protocol and meeting the definition of a SAE must be reported to the IRB in accordance with the timeframes and procedures outlined in

“University of Texas M. D. Anderson Cancer Center Institutional Review Board Policy on Reporting Serious Adverse Events”. Unless stated otherwise in the protocol, all SAEs, expected or unexpected, must be reported to the IND office, regardless of attribution (within 5 working days of knowledge of the event).

- All life-threatening or fatal events, expected or unexpected, and regardless of attribution to the study drug, must have a written report submitted within 24 hours (next working day) of knowledge of the event to the IND office
- The MDACC “Internal SAE Report Form for Prompt Reporting” will be used for reporting to the IND office.
- Serious adverse events will be captured from the time the patient signs consent until 30 days after the last dose of drug. Serious adverse events must be followed until clinical recovery is complete and laboratory tests have returned to baseline, progression of the event has stabilized, or there has been acceptable resolution of the event.
- Additionally, any serious adverse events that occur after the 30 day time period that are related to the study treatment must be reported to the IND office. This may include the development of a secondary malignancy.

7.2.4.2.2.4. Reporting to FDA:

- Serious adverse events will be forwarded to FDA by the IND Office, according to 21 CFR 312.32.

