- 7.2.13. Surgery: Following successful completion of presurgical therapy, patients will undergo radical nephrectomy (open or laparoscopic at the surgeon's discretion), with retroperitoneal lymph node dissection. Extent of lymph node dissection will be recorded in the operative record and should include the ipsilateral nodes from renal hilum to aortic bifurcation, as well as the interaortocaval nodes from renal hilum to aortic bifurcation. Primary tumor specimens will be immediately sent to pathology on ice for further processing and correlative study specimen harvest. Routine perioperative parameters will be recorded and will include operative approach, operative time, estimated blood loss, ease of surgical dissection, comment on tissue planes, intraoperative complications (with grade), post-operative complications (with grade), blood transfusions, length of ICU stay (if applicable), length of hospital stay, perioperative mortality (within 30 days of surgery). The operating urologist will make a decision based on their extensive surgical expertise if these adverse events are attributable to axitinib or not. These events will certainly be monitored and recorded by the operating urologist, and discussed with the IND if they arise.

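### The two-death stopping rule in 6.1 counts only deaths the Principal Investigator attributes to axitinib, without stated criteria; a recruitment pause at the second death from any cause should be added

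*Combined protocol and SAP*

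**What the plan says.** Section 6.1 sets the rule: "We plan to stop recruitment if we observe 2 treatment-related deaths". It then limits what counts: "Treatment-related deaths are defined as deaths directly caused by study drug while the patients are taking the study drug, or intraoperatively". A third window covers the 30 days following surgery. One person decides: "the decision to classify the deaths as directly caused by study drug will be made by the study Principal Investigator".

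The next sentence gives the only reference rate: "Perioperative mortality for patients undergoing radical nephrectomy is estimated to be between 1% and 4" percent. Table 3 follows, indexed by treatment-related mortality from 0.005 to 0.2.

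The following paragraph of 6.1 also stops recruitment when two or more patients meet any of four further conditions. Two of these are fascial dehiscence requiring reoperation and postoperative bleeding requiring reoperation. Neither has to be attributed to the drug.

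Section 7.2.13 lists 30-day perioperative mortality among the recorded surgical parameters and adds: "The operating urologist will make a decision based on their extensive surgical expertise if these adverse events are attributable to axitinib or not". Section 7.2.4.1.1 gives attribution of adverse events in general to the investigator.

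Reporting is separate from the rule. Under 7.2.4.2.2.3, "All life-threatening or fatal events, expected or unexpected, and regardless of attribution to the study drug, must have a written report submitted within 24 hours" to the IND Office.

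**The concern.** The trial has one arm, and axitinib is taken until 1.5 days before major surgery. With no concurrent control, there is often no reliable way to say whether a postoperative death came from the drug or the operation. The rule rests on that judgment. It does not say what makes a death directly drug-caused, and it does not tie the term to the five-level relationship scale in 7.2.4.1.3. Whether a death rated possible or probable counts is therefore undefined.

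Two things follow. First, the 1% to 4% figure describes nephrectomy patients in general, so it does not help a reader judge whether two attributed deaths in 24 is a strict or a lax limit. Second, the more severe outcome can face the harder test. A bleed that needs reoperation counts automatically. A fatal bleed without reoperation, or a fatal clot, counts only if it is attributed to the drug. If axitinib raised mortality through ordinary surgical complications, the rule could respond late or not at all.

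**Working it through.** **Inputs.** Boundary of 2 deaths and maximum of 24 patients (6.1: "Twenty-four patients will be treated in this study"). Stopping probabilities from Table 3 ("These probabilities were derived by running 1,000 simulations"). Background of 1% to 4% (6.1). The share *f* of deaths classified as drug-caused is not in the documents; 100%, 75%, 50% and 25% are assumed.

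**Step 1: reproduce Table 3.** With *q* the rate of deaths that count,

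P(stop) = 1 − (1 − q)^24 − 24 q (1 − q)^23.

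| q | Table 3 | Exact |
|---|---|---|
| 0.005 | 0.012 | 0.006 |
| 0.01 | 0.033 | 0.024 |
| 0.02 | 0.083 | 0.083 |
| 0.04 | 0.268 | 0.249 |
| 0.07 | 0.505 | 0.508 |
| 0.1 | 0.708 | 0.708 |
| 0.2 | 0.976 | 0.967 |

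All seven agree within 0.02. No difference exceeds about 2.2 Monte Carlo standard errors for 1,000 runs. The table is sound for the rate it indexes.

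**Step 2: let only a share of deaths count.** If total mortality in the rule's windows is *p*, the counted rate is q = p × f.

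- p = 0.10, f = 1: q = 0.10, and 1 − 0.0798 − 0.2127 = 0.708.
- p = 0.10, f = 0.5: q = 0.05, and 1 − 0.2920 − 0.3688 = 0.339.

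| Total mortality p | f = 1 | f = 0.75 | f = 0.5 | f = 0.25 |
|---|---|---|---|---|
| 4% | 0.249 | 0.161 | 0.083 | 0.024 |
| 7% | 0.508 | 0.361 | 0.205 | 0.066 |
| 10% | 0.708 | 0.546 | 0.339 | 0.120 |
| 20% | 0.967 | 0.894 | 0.708 | 0.339 |

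**Step 3: count every death when the drug adds none.** At background rates of 1% and 4%, the chance of reaching two deaths is 0.024 and 0.249 (Table 3: 0.033 and 0.268). These rates are perioperative only. If deaths before surgery added 1 percentage point (an assumption), the exact values at 2% and 5% would be 0.083 and 0.339.

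**Step 4: compare the reporting window with the rule's window.** Section 7.2.4.2.2.3 captures serious adverse events until 30 days after the last dose, and after that only related ones. The rule runs to 30 days after nephrectomy. With the last dose 1.5 days before surgery, the windows differ by at least 1.5 days, and by more if surgery is delayed.

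**The case against.** The best defence is that attribution is a deliberate trade-off. If every death led to a stop, a harmless drug would close the trial about 25% of the time at 4% background mortality. On that reading, the 1% to 4% figure explains why surgical deaths are left out, and no boundary is derived from it. This stands as a reason to keep the present stop and not turn it into an all-cause stop. It does not supply the missing criteria.

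Part of the fall in Step 2 is also what the rule intends. If mortality adds simply, 10% total over a 1% to 4% background leaves 6 to 9 points due to the drug, so even perfect attribution would give a share of 60% to 90%, not 100%.

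The attribution-free rules on dehiscence and bleeding do cover part of the surgical harm, and before death. They do not reach a fatal clot or a fatal complication without reoperation.

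Three stronger readings may tempt a reader, and the documents do not support them:

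- *Table 3 is wrong, or valid only if every death is attributed.* It is indexed by the same quantity that the rule counts, and it reproduces. What is uncertain is which row applies.
- *Two people hold the deciding vote.* For the stopping rule, 6.1 names only the Principal Investigator. Section 7.2.13 concerns recorded perioperative events and does not mention the rule. What is missing is a statement of how the two attributions relate.
- *Deaths could go unseen.* Fatal events go to the IND Office whatever their attribution, 30-day perioperative mortality is recorded, and 7.2.13 events are discussed with the IND. Deaths can go uncounted only toward this one rule.

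**Conclusion.** The point holds as a gap in the definition and scope of the mortality rule, not as an arithmetic error. The count depends on one person's judgment without stated criteria, in a design that gives little basis for making it. The cited background rate is not comparable with the rate in Table 3. Some fatal complications fall outside monitoring that applies to non-fatal ones.

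The size depends on the share of deaths classified as drug-caused, which the documents do not give. At half, the chance of stopping falls from 0.71 to 0.34 at 10% mortality and from 0.51 to 0.21 at 7%. These figures illustrate sensitivity and do not predict how the Principal Investigator would classify deaths. The calculation treats patients as independent and applies the rule up to the 24th patient. The gap justifies an inexpensive change of wording, not a redesign.

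**What to change.** Keep the existing stop at two treatment-related deaths and make four changes.

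1. Add to 6.1 that recruitment pauses for IND Office review at the second death from any cause on study drug, during surgery or within 30 days after nephrectomy. State the basis on which recruitment may resume.
2. Require all deaths to be reported through 30 days after nephrectomy, so that reporting covers the rule's full window.
3. State that the 1% to 4% rate applies to the all-cause perioperative count and not to the drug-attributed count behind Table 3. Deaths on drug before surgery are not part of that rate.
4. Reconcile 6.1 with 7.2.13 by stating that the operating urologist's attribution does not determine the count for the rule.

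The change concerns recruitment only. It needs protocol wording and almost no new data, because fatal events already go to the IND Office and 30-day mortality is already recorded. It does give the IND Office a review task that the documents do not now assign to it. The statistical cost is about a 2% to 25% chance of a pause on background perioperative mortality alone (exact binomial; Table 3 gives 3% to 27%), and somewhat more once deaths before surgery are included. Because the new trigger leads to a review and not to closure, that cost is limited, and the present firm stop is not weakened.
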